## **6.3 Exploratory objectives**

Commercially Confidential Information

Commercially Confidential Information

Commercially Confidential Information

## **7 Statistical methods for safety and tolerability data**

All safety presentations and analyses will be based on the Safety Analysis Set.

### **7.1 Variables**

Adverse events, vital signs (blood pressure, pulse rate, respiratory rate, body temperature, peripheral oxygen saturation, oxygen flow rate and/or FiO2), ECG intervals, safety laboratory measurements, as well as subject demographics, baseline characteristics, and treatment information.

### **7.2 Descriptive analyses**

Safety summaries (tables, figures) include only data from the on-treatment period with the exception of baseline data, which will also be summarized where appropriate (e.g. change from baseline summaries).

The on-treatment period lasts from the date of randomization to Day 29.

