3. **Follow-up** (Day 16-29): After completion of the 14 day- treatment period, participants will be observed until Day 29 or discharged from hospital, whichever is sooner. Study assessments to be conducted every 2 days for hospitalized participants. If participants are discharged from hospital prior to Day 29, a study visit conducted by telephone will occur on Day 29 (all other visits between discharge and Day 29 can be omitted).
4. **30-day safety follow-up assessment** (Day 45): A follow-up visit for safety will be conducted by telephone.

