## 4.2 Unscheduled visits

Data collected at unscheduled visits will be used to replace missing values if a Last observation carried forward (LOCF) approach is applied within the allowed LOCF period of maximum 4 days (i.e. for the mortality scores APACHE II, Commercially Confidential Information as described in [Sections 6.1.6](#) and [Section 6.3.1](#)).

In addition for the screening/baseline visit unscheduled assessments within 24 hours prior to signing the Informed Consent Form (ICF) can be used.

For other type of analyses and other visits no unscheduled visits data will be considered.

Commercially Confidential Information

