#### **7.2.4 ECG evaluations**

Heart rate, PR, QRS, QT, QTcF, and RR intervals will be obtained from ECGs (12-lead or 5-lead) for each participant during the study. ECG data will be read and interpreted locally.

Categorical analysis of QT/QTcF interval data based on the number of participants meeting or exceeding predefined limits in terms of absolute QT/QTcF intervals or changes from baseline will be presented.

Summary statistics will be provided by treatment group and visit/time.

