## Commercially Confidential Information

**7.2.6 Adverse events**

All information obtained on adverse events will be listed by treatment and subject.

Summary tables for adverse events (AEs) will summarize only on-treatment events, with a start date during the on-treatment period (treatment-emergent AEs).

The number and percentage of subjects with adverse events will be tabulated by body system and preferred term with a breakdown by treatment. Separate summaries will be provided for study medication related adverse events and other significant adverse events leading to discontinuation.

The number of deaths resulting from SAEs suspected to be related to study treatment and SAEs irrespective of study treatment relationship will be provided by SOC and PT.

A subject with multiple adverse events within a body system is only counted once towards the total of this body system and treatment.

For the legal requirements of ClinicalTrials.gov and EudraCT, two tables are required: on treatment emergent adverse events which are not serious adverse events and on treatment emergent serious adverse events and SAE suspected to be related to study treatment will be provided by system organ class and preferred term on the safety analysis set.

If for a same patient, several consecutive AEs (irrespective of study treatment causality, seriousness and severity) occurred with the same SOC and PT:

- a single occurrence will be counted if there is  $\leq 1$  day gap between the end date of the preceding AE and the start date of the consecutive AE
- more than one occurrence will be counted if there is  $> 1$  day gap between the end date of the preceding AE and the start date of the consecutive AE.

For occurrence, the presence of at least one SAE / SAE suspected to be related to study treatment / non SAE has to be checked in a block e.g., among AE's in a  $\leq 1$  day gap block, if at least one SAE is occurring, then one occurrence is calculated for that SAE.

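### AEs and SAEs starting on Days 30-45 are listed but not tabulated by arm, and QT/QTcF exceedances seen only at unscheduled ECGs are not counted

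*SAP*

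**What the plan says.** **The tabulated period.** SAP section 7.2 states: "Safety summaries (tables, figures) include only data from the on-treatment period with the exception of baseline data". It then sets the limit: "The on-treatment period lasts from the date of randomization to Day 29". Section 7.2.6 repeats the restriction for adverse events: "Summary tables for adverse events (AEs) will summarize only on-treatment events, with a start date during the on-treatment period". The two registry tables described there are also of treatment-emergent events. The death table in the same section has no window of its own, so the general rule of section 7.2 governs it.

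**The collection period.** Section 1.4 places the end-of-treatment visit on Day 15 and adds, as the fourth part of the study, a 30-day safety assessment at Day 45: "A follow-up visit for safety will be conducted by telephone".

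**Listings.** Section 7.2.6 sets no time limit here: "All information obtained on adverse events will be listed by treatment and subject".

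**Unscheduled data.** Section 4.2 allows unscheduled values for two purposes: carrying forward components of the mortality scores, and the screening/baseline visit. It then closes the door: "For other type of analyses and other visits no unscheduled visits data will be considered". Sections 7.2.3 to 7.2.5 (vital signs, ECG, laboratory) make no exception. Section 7.2.4 nevertheless plans a count of participants "meeting or exceeding predefined limits in terms of absolute QT/QTcF intervals or changes from baseline will be presented".

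**The concern.** Two rules, each simple to state, make the by-arm safety counts smaller than the recorded data would support.

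First, the trial follows participants for safety for 30 days after end of treatment but tabulates roughly the first half of that time. The safety endpoint in Table 1-1 is a number of participants with AEs and SAEs. A listing shows individual events but gives no count or percentage per arm. In hospitalised COVID-19 pneumonia, where the primary endpoint itself imputes for death, late SAEs and deaths are events a reader will want compared between arms.

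Second, a threshold table answers whether a participant ever crossed a limit. If the SAP ignores an exceedance because the ECG was unscheduled, the table reports that participant as free of it although the database shows otherwise.

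**Working it through.** The SAP has no figure to reproduce here. The check is a side-by-side reading with a day count.

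**A. The window**

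Inputs: end of treatment Day 15, safety follow-up Day 45 (both section 1.4), end of tabulated period Day 29 (section 7.2).

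- Check on the follow-up label: 15 + 30 = 45, so Day 45 is 30 days after the end-of-treatment visit.
- Days collected but not tabulated: 45 - 29 = 16 (Days 30-45).
- Share of Day 1 to Day 45: 16/45 = 35.6%.
- Share of the 30 days after end of treatment (Days 16-45): 16/30 = 53.3%. The other 29 - 15 = 14 days (46.7%) are tabulated.

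The SAP gives no event rates, so the 35.6% converts to events only under an assumption. With a constant onset rate, about 36% of onsets would fall outside the tables. With onset falling over time, the share would be lower.

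**B. Does another visible table fill the gap?**

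- Disposition (section 7.2.1) reports completion at Day 15 and Day 29.
- The ordinal clinical status scale (section 6.2.1) carries death forward to Day 29 and no further.
- The death table (section 7.2.6) concerns deaths resulting from SAEs. If it follows the start-date rule, a death from an SAE starting after Day 29 is outside it. For a death after Day 29 from an SAE that began by Day 29, the text does not settle the matter.
- No all-cause death table to Day 45 is visible.

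**C. Unscheduled ECGs**

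Set section 4.2 beside section 7.2.4. Consider a participant whose scheduled ECGs are all below a limit and who has one unscheduled post-baseline ECG above it. Section 4.2 removes that ECG, so the participant is counted as not exceeding the limit. Admitting unscheduled post-baseline values, with baseline unchanged, can only leave each count the same or raise it. Section 1.4 makes the situation plausible after discharge, because intermediate visits may be omitted and the Day 29 visit is then by telephone. The frequency cannot be derived from the SAP.

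**D. Laboratory data**

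The visible text of section 7.2.5 plans summary statistics by visit and no abnormality or worst-value table. Redacted text follows. No loss can therefore be shown for laboratory values. It can only be said that any such count, if planned, would fall under section 4.2.

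**The case against.** The strongest reply is that Day 29 is a legitimate choice. Table 1-1 sets no time window for the safety endpoint, so the cut contradicts nothing. Day 29 is two weeks past the end-of-treatment visit. The Day 45 contact is a telephone call, so the cut loses no ECG, laboratory or vital-sign data from that contact. Late AEs are still listed by treatment. For unscheduled data, keeping by-visit summaries to scheduled visits is sound. In an open-label trial against SoC alone, more testing in one arm could inflate its exceedance count.

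Much of this stands. The Day 29 cut is not an internal contradiction and can be kept, and by-visit summaries should stay on scheduled visits. It does not follow that collected late events need no count by arm, since a Day 45 summary can sit beside the Day 29 one. Unequal testing is a reason to show both counts, not to drop recorded exceedances.

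A reader might infer more than the SAP supports:

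- *That Day 30-45 events vanish from the report.* They do not; they are listed by treatment and subject.
- *That all deaths after Day 29 are left out.* This is not established for deaths from SAEs that began earlier.
- *That the worst QTcF and laboratory values are dropped.* Extremes at scheduled visits up to Day 29 are kept, and no laboratory worst-value table is visible.
- *That 36% of events are lost.* The figure is a share of days.

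**Conclusion.** The point holds in two limited parts.

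1. AEs and SAEs starting on Days 30-45, and deaths from them, are listed only and enter no summary by arm. The untabulated stretch is 16 of 45 days, or 16 of the 30 days after end of treatment. The handling of a death after Day 29 from an earlier SAE is left open. This rests on the Day 45 safety contact recording AEs and SAEs, as its description implies; its detailed content would be in the protocol, which is not at hand. It also rests on no redacted section supplying a Day 45 table.

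2. A QT/QTcF limit exceeded only at an unscheduled ECG is not counted in the categorical table. The direction is certain (the count is the same or too low), but the size is unknown.

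Neither part touches the primary analysis. Both should be corrected, because the rules as written under-count by arm and the correction needs no new data.

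**What to change.** - **Sections 7.2 and 7.2.6:** add AE, SAE and all-cause death summaries by arm from randomisation to Day 45, and keep the Day 29 cut alongside. State whether a death is placed by its own date or by the start date of the causal SAE.
- **Section 4.2:** exempt the QT/QTcF categorical counts, and any laboratory or vital-sign abnormality counts that are planned, so that they use all post-baseline values, scheduled and unscheduled. Leave by-visit summaries on scheduled visits.
- **Open-label caveat:** show scheduled-only counts beside the all-value counts, or footnote any imbalance between arms in unscheduled testing.

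The cost is SAP wording, a second date cut-off in programming and a few extra tables. The statistical downside is small: testing frequency may differ between the open-label arms, which the parallel counts or the footnote make visible.

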#### **7.2.1 Subject demographics and other baseline characteristics**

##### **Screen failures with SAEs**

For screen failed participants in case the participant experienced a serious adverse event during the screening phase the following information is captured and listed: demographic information, informed consent, as well as information on SAEs. Inclusion/Exclusion criteria will be summarized.

## Disposition

The following disposition status will be summarized as the number and percentage of participants

- who were screened but not randomized (percentage based on all screened participants)
- who were randomized (percentage based on all screened participants)
- who were discharged prior to day 15 and day 29 respectively
- who completed the study until day 15 and day 29 respectively
- who discontinued from study (overall and by the primary reason for discontinuation).

The number and percentage of participants included in each analysis set will be tabulated by treatment group. Participants excluded from an analysis sets will be listed with reasons for exclusion (i.e. including both protocol and non-protocol deviations).

Unless otherwise stated any percentages are based on the respective number of randomized participants.

## Demographic and Baseline characteristics

Demographic characteristics, including gender, race, ethnicity, age, age categories (<65 and ≥ 65 years), height, body weight at screening, body categories (40 to <60 kg, 60 to <80 kg, 80 to <100 kg, 100 to <120 kg, ≥120 kg), body mass index (BMI) at screening, BMI categories (≤ 30.0 kg/m^2 and > 30.0 kg/ m^2), country will be summarized with descriptive statistics by treatment and overall. Body mass index (BMI) will be calculated using the following formula:

- $BMI = \text{Body weight (kg)} / [\text{Height (m)}]^2$

The Screening visit height measurement will be used for BMI calculations throughout the study.

The number of days between the onset of symptoms to start of treatment will be listed.

The summary of the following baseline disease characteristics will be provided by treatment group:

Commercially Confidential Information

- Chest X-ray or CT scan interpretation (Normal/Abnormal/not available)
- Clinical status based on the 9-point ordinal scale (Score=0, 1, ..., 8)
- Use of corticosteroid at the time of randomization (based on prednisone equivalent dose see [Section 10.7](#))
- Use of anti-viral treatment at the time of randomization (Yes, No) and by type of anti-viral treatment (e.g. hydroxychloroquine, chloroquine, remdesivir, faripivavir, ritonavir, lopinavir, convalescent plasma)
- Number and presence of the following comorbidities: diabetes, hypertension, cardiovascular disease (i.e. chronic heart disease), chronic lung disease (e.g. COPD, asthma)
- Baseline Oxygen use based on the type of pulmonary/ventilatory support (defined in [Table 6-1](#))

- Marker for inflammation as continuous variables: CRP,  
Commercially Confidential Information
- The distribution of the three stratification parameters will be summarized separately by treatment group.

For oxygen requirement at baseline the type of support required prior but closest to the day of randomization will be reported.

Protocol deviations will be listed and summarized by treatment group.

All medical history including the comorbidities will be listed.

### **7.2.2 Treatment**

The duration of exposure to DFV890 in days will be summarized as well as the number and percentage of participants with treatment compliance of <80% and ≥80% respectively.

Concomitant medications and significant non-drug therapies prior to and after the start of the study treatment will be listed and summarized according to the Anatomical Therapeutic Chemical (ATC) classification system by treatment group. For corticosteroids ATC-Subclasses will be added. Convalescent plasma treatment will included in the anti-viral treatment presentations.

For any of the below mentioned three treatment categories, if it started prior to randomization and continued during the study, it will be reported under baseline as well as part of SoC during study participation.

#### **Corticosteroids use**

The number and percentage of patients will be summarized by treatment group for the following parameters:

- receiving any corticosteroids after randomization
- receiving corticosteroid for treatment of Covid-19 after randomization
- receiving Dexamethasone after randomization reporting the highest total daily dose observed during the study using the following ranges:  
<6 mg, 6-<12 mg, ≥ 12 mg

The following presentations will be based on the prednisone equivalent dose (see Appendix for details):

- with a change in their corticosteroids dose after randomization (increased/reduced/stable dose)
- receiving corticosteroids after randomization reporting the highest total daily dose observed during the study using the following ranges:  
<7.5 mg, 7.5-<20 mg, ≥ 20 mg

#### **Anti-viral medication use**

The number and percentage of patients will be summarized by treatment group for the following parameters:

- receiving any anti-viral medication after randomization

- receiving anti-viral medication for treatment of Covid-19 after randomization
- receiving hydroxychloroquine/chloroquine/remdesivir/faripivavir/ritonavir/lopinavir/convalescent plasma after randomization receiving a combination of the above anti-viral medications after randomization tabulated by all combinations actually occurring.

### **Anti-coagulation therapy**

The number and percentage of patients will be summarized by treatment group for the following parameters:

- receiving any anti-coagulation medication after randomization
- receiving anti-coagulation medication for treatment of Covid-19 after randomization

### **Combination of SoC medications**

The number and percentage of patients receiving any combination of steroids, anti-viral and/or anti-coagulants treatments after randomization will be summarized by treatment group.

#### **7.2.3 Vital signs**

Vital sign measurements include respiratory rate, pulse rate (PR), systolic and diastolic blood pressure, mean arterial pressure body temperature, weight and BMI. Peripheral oxygen saturation on room air or on supplemental oxygen is also measured at the same time as the vitals. In case oxygen saturation is reported for both room air and under supplemental oxygen, the value for room air is included in summary presentations and analysis. For participants requiring supplemental oxygen, the oxygen flow rate (L/min) and/or FiO2 is also recorded.

Summary statistics will be provided by treatment group and visit/time.

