**7.2.7 Graphical presentation**

For all vital signs, ECGs and laboratory parameters the following graphical presentations will be provided:

Panels of individual spaghetti plots over time for each parameter and their change from baseline will be drawn. The profiles of all participants in the respective treatment group will be included in these graphs as grey lines in the background and the respective individual participants profile will be plotted with darker color in the foreground. The respective applicable normal ranges will be added and it will be indicated by a symbol if a patient died.

Means (+/- SE) will be plotted over time by treatment group.

Commercially Confidential Information

---

Commercially Confidential Information

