### 4. Respiratory Rate (breaths per minute)

### 5. Oxygenation: depending on the Fraction of inspired Oxygen (FiO2, where FiO2 is a value between 0 and 1 (i.e. not on % scale)):

- If FiO2 < 0.5: use PaO2 (mmHg)
- If FiO2 >= 0.5: use A-aDO2 (mmHg): where A-aDO2 is calculated as  $A-aDO2 = (FiO2 \times 713 - PaCO2/0.8) - PaO2$

In case PaO2 is not available for a certain visit it can be derived from SPO2 if available instead using the following conversion table:

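### The SpO2 displays implicitly mix room-air and on-oxygen values, so weaning can look like worsening and a difference between arms in oxygen need can be diluted or, in some conditions, reversed

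*SAP*

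**What the plan says.** SAP Section 7.1 lists SpO2 once among the vital signs, next to the oxygen variables: "peripheral oxygen saturation, oxygen flow rate and/or" FiO2. Section 7.2.3 allows two measurement conditions: "Peripheral oxygen saturation on room air or on supplemental oxygen is also measured at the same time as the vitals". Its only selection rule is for assessments with both values, where "the value for room air is included in summary presentations and analysis". Flow rate and/or FiO2 is recorded for participants who need oxygen. The layout is then fixed without reference to the oxygen condition: "Summary statistics will be provided by treatment group and visit/time".

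Section 7.2.7 covers all vital signs. It plans individual profiles of the value and of its change from baseline, and for the arms: "Means (+/- SE) will be plotted over time by treatment group". Section 7.2 also foresees change-from-baseline summaries where appropriate. Section 4.1 takes baseline as the last assessment up to randomization and does not require the oxygen condition to match that of later visits.

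**The concern.** A rule that picks one value per assessment makes sense only if SpO2 is analysed as a single variable. At an assessment with only one value, that value enters, whether it was taken on room air or on oxygen. The two do not measure the same thing, because oxygen is given to bring SpO2 up. The room-air preference reduces the mixing where both values exist. It does nothing for patients who cannot be taken off oxygen and so probably have only an on-oxygen value.

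Two displays are affected. In the individual plots, a move between conditions changes SpO2 for reasons other than lung function. In the arm means, the arm with more patients on oxygen contributes more oxygen-supported values. The trial enrols patients with COVID-19 pneumonia and impaired respiratory function, so readers of the safety section will look at these displays directly.

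**Working it through.** The SAP gives no figure on this point to reproduce. The checks below are illustrations. All SpO2 values, oxygen shares, FiO2 and PaCO2 are assumptions; the A-aDO2 formula and the SpO2-to-PaO2 conversions come from SAP Section 10.2, item 5 and Table 10-1.

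**1. Individual change from baseline.** Assume FiO2 0.21 on room air, FiO2 0.40 on oxygen and PaCO2 40 mmHg. A-aDO2 = (FiO2 × 713 − PaCO2/0.8) − PaO2. The SAP scores A-aDO2 only at FiO2 of 0.5 or more; here it serves only as a measure of gas exchange.

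- Weaned, 95% on oxygen to 93% on room air (PaO2 79 to 69):
  - SpO2 change: −2 points.
  - A-aDO2: 285.2 − 50 − 79 = 156, then 149.7 − 50 − 69 = 31 mmHg (better).
  - SpO2/FiO2: 95/0.40 = 238, then 93/0.21 = 443 (better).
- Escalated, 92% on room air to 96% on oxygen (PaO2 65 to 86):
  - SpO2 change: +4 points.
  - A-aDO2: 149.7 − 50 − 65 = 35, then 285.2 − 50 − 86 = 149 mmHg (worse).
  - SpO2/FiO2: 92/0.21 = 438, then 96/0.40 = 240 (worse).

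In both cases the SpO2 change has the wrong sign, and a measure that takes account of FiO2 has the right one. The A-aDO2 directions are the same at PaCO2 30 and 50 mmHg.

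**2. Arm means.** Let q be the share of an arm with only an on-oxygen value, o the mean SpO2 on oxygen and r the mean on room air. The pooled mean is q·o + (1 − q)·r, so the difference between arms (B, with more oxygen need, minus A) is (qB − qA)(o − r).

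- With o = 96, r = 94 and shares of 30% and 50%: 0.3 × 96 + 0.7 × 94 = 94.6 and 0.5 × 96 + 0.5 × 94 = 95.0. Arm B looks 0.4 points better.
- For comparison on a common room-air basis, assume that patients on oxygen would have 88% off it. The difference is then (qB − qA)(88 − r). With shares of 20% and 40%, o = 95 and r = 94, the pooled difference is +0.2 and the room-air difference is −1.2. With shares of 30% and 60% they are +0.3 and −1.8.
- Over o from 93 to 97, r from 93 to 95 and both pairs of shares, the pooled difference runs from −0.6 to +1.2 points, against −1.0 to −2.1 on room air.

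The sign of the pooled difference is the sign of o − r. It reverses the arms only when o > r, is zero when o = r, and otherwise shows the right direction but too small a gap.

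**3. APACHE II.** Section 10.2, item 5 says: "In case PaO2 is not available for a certain visit it can be derived from SPO2 if available instead". It does not say that this SpO2 must come from the same oxygen condition as the FiO2. At FiO2 0.5 and PaCO2 40, A-aDO2 = 356.5 − 50 − PaO2 = 306.5 − PaO2. SpO2 98% (PaO2 112) gives 194.5, scored 0. A room-air SpO2 of 88% (PaO2 55) set against the same FiO2 gives 251.5, scored 2.

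**The case against.** The strongest reply is that the SAP nowhere states that the two conditions are pooled. The one rule it has lessens the mixing, and a programmer could still split the table. This stands in part: pooling is an implication, although no text prevents it and the listed layout has no place for a split.

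A reader might infer that the plan hides respiratory deterioration. The document does not support that. Flow rate and/or FiO2 are safety variables in their own right. The 9-point scale separates no oxygen, mask or prongs, non-invasive or high-flow support, and intubation; it is summarized by arm and visit and shown patient by patient in a heat map. Parts of the SAP are redacted, so further respiratory analyses may exist. No hypothesis test uses the SpO2 summaries.

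A reader might also infer that arm-level changes from baseline will have the wrong sign. Section 7.2.7 plans change from baseline only as individual profiles, and Section 7.2 foresees change summaries only where appropriate, so an arm-level SpO2 change table is not clearly planned.

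Finally, a reader might carry the room-air rule into the primary endpoint. That rule sits in the safety part, and nothing extends it to the APACHE II appendix. The example also needs PaO2 missing while PaCO2 is available, FiO2 of at least 0.5 and a room-air SpO2 at the same visit, which is probably uncommon.

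**Conclusion.** The point holds as a limited fault of presentation. Followed as written, Sections 7.2.3 and 7.2.7 put room-air and on-oxygen SpO2 into one variable. An individual patient's change can then point the wrong way (−2 while improving, +4 while worsening in the examples). A difference between arms in oxygen need is diluted, and is reversed only if on-oxygen SpO2 exceeds room-air SpO2. The sizes rest wholly on assumed inputs, and nothing in the SAP shows that reversal is likely. The displays are descriptive and oxygen need can be read elsewhere, but those other outputs do not correct the SpO2 displays themselves. For APACHE II, at most a one-line clarification is warranted.

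**What to change.** In Sections 7.2.3 and 7.2.7:

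- Present SpO2 by oxygen condition (room air, supplemental oxygen), with the number and percentage on oxygen per arm and visit beside each mean.
- Mark the oxygen condition at each point of the individual plots.
- Flag changes from baseline where the condition differs, and keep those patients. Limiting change to like conditions would remove the weaned and escalated patients, who are the most informative.
- Where FiO2 is recorded, add SpO2/FiO2 for all patients, stating the FiO2 assigned to room air.

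In Section 10.2, item 5, add one line saying that the converted SpO2 and the FiO2 come from the same condition.

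The cost is SAP wording and some extra table columns and plots. No new data are needed, since the SAP already has oxygen condition and flow rate and/or FiO2 recorded; SpO2/FiO2 will be missing where only flow was captured. Numbers per stratum will be smaller. The strata are defined after randomization, so their arm means should be labelled descriptive and not read as randomized comparisons.
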